# Study design and methods

- A. The primary aim of this study is to compare the reliability of self-collected specimens versus physician-collected specimens in detecting high-risk HPV. This clinical trial is being carried out at multiple centers in Taiwan with laboratory technicians being blind of the sample sources.
- B. The trial aims to assess how well regular women can collect specimens using self-collection kits without professional assistance
- C. To ensure effective specimen collection by ordinary women, visual aids and pre-recorded audio and video materials will be provided for self-learning. Participants will then answer a questionnaire to verify the clarity of the instructional materials. Before HPV testing, the laboratory will verify the specimen's integrity by testing for beta-globin DNA.
- D. Subject inclusion procedures:
- 1. Eligible women who agree to participate will sign a consent form after receiving an explanation from the doctor.
- 2. Once the predetermined number of participants is reached, no further subjects will be enrolled, and the test results will be revealed and analyzed statistically.
- E. Sample collection procedure:
- 1. After obtaining consent, the study nurse will provide a coded self-sampling swab to each subject for self-collection. Cervical cell collection by the physician will follow routine procedures in the outpatient clinic. The self-sampling swabs are randomly coded to ensure blinding for laboratory test operators.
- 2. Physician examination:
- (1) Doctors use a cytological brush to collect cervical cells in accordance with medical routine during the outpatient clinic.
- (2) The specimens collected for examination will be kept by nurses and sent to the National Tsing Hua University laboratory.
- (3) Vaginal lavage or intravaginal medication should be avoided before specimen collection. Additional tests like smear examination or colposcopy may be conducted if necessary.
- 3. Self-sampling:
- (1) Subjects will receive a "HygeiaTouch Self-sampling Kit for Women" containing a sterile self-sampling swab and sample collection tube. They must read the instruction manual, watch an instructional video, and confirm their understanding by answering questions.
- (2) After self-sampling, subjects will place the swab in the collection tube and hand it to the study nurse.

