- (3) When collecting self-sampled specimens from subjects, the study nurse asked the subjects to complete the self-sampling questionnaire in the case report form and provided assistance. After the subjects fill out the questionnaire, the research nurse will take back the case report form.
- (4) Subjects can self-sampling on the day of the outpatient clinic or thereafter, but no biopsy, medicine, surgery or any form of treatment is allowed between the subject's self-sampling and the doctor's sampling. The self-collected specimens are placed into the collection tube of the set and stored at room temperature. Specimens must be sent to the study nurse within one week of collection.
- F. Specimen number and test results:
- 1. Test work bag:
- (1) In order to facilitate the conduct of the trial and avoid confusion and errors, each subject will be assigned a trial work bag with a subject number on it according to the order of inclusion in the trial after signing the subject consent form.
- (2) The test work bag contains:
- ♦ 1 copy of "Libo cytological Brush (set)" for medical examination
- Self-sampling: 1 copy of "HygeiaTouch Self-sampling Kit for Women"
- ♦ 1 copy of subject consent form
- ♦ 1 case report form
- 2. Physician collects specimens:
- (1) When conducting outpatient examinations, doctors will use test work bags marked with subject numbers according to the order in which subjects are included.
- (2) The subject number has been marked with a sticker on the collection tube of each "Libo Libo cytological Brush (Set)".
- (3) This subject number is the specimen number collected by the doctor.
- (4) In the experimental laboratory, samples are examined for HPV typing, and the results will be shared with doctors for clinical purposes. These results will be given to patients and used as a benchmark for consistency comparison in the study.
- 3. Self-collected samples from subjects:
- (1) The serial number of the self-collected specimen has been marked with a sticker on the specimen collection tube of each "HygeiaTouch Self-sampling Kit for Women".
- (2) The self-collected sample number is a number obtained by random garbled calculation based on the sample number collected by the physician. This number cannot directly determine the correlation between the specimen collected by the physician and the specimen collected by the subject.

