## Secondary evaluation indicators to be analyzed

- A. Evaluation of the success rate (proportion of effective specimens) of HPV typing by doctors ' samples and self- collected samples of all detectable HPV types.
- B. Consistency assessment will take valid samples as the analysis group, that is, the same subject's verification physician and self- sampling samples are all valid samples. A valid sample is defined as a positive test for the  $\beta$  -globin gene in the internal control group of Jingyu Human Papillomavirus Genotyping Detection Kit . The intent-to-treat group (ITT) was used as the analysis group for safety, self- collection success rate, and satisfaction evaluation.
- C. used as a safety evaluation index to evaluate whether there will be adverse reactions (such as psychological discomfort or other physical discomforts) in the self - examination of vaginal secretions by doctors or by women .
- D. Evaluate whether women can complete effective self-specimen sampling by following the instructions or videos. The beta-globin of the test results will be used as an evaluation index for valid specimens, and the reliability of the explanatory files will be evaluated by the results of the questionnaire survey.

- E. -collection success rate (proportion of effective specimens) and consistency evaluation of each group under the test group .
- F. The correlation between the HPV test results collected by physicians , the HPV test results of self-collected samples, and the results of Pap smear and histopathological diagnosis at the same time . Taking the most serious pathological diagnosis as the standard, calculate :
  1. the sensitivity, specificity, positive predictive value and negative predictive value of cervical lesions based on the HPV test results of the samples taken by doctors
  2. the sensitivity, specificity, positive predictive value and negative predictive value of cervical lesions based on the test results of self- collected samples
- G. Use the subject questionnaire in the case report form to collect the survey data of the subject's self- test satisfaction survey, and conduct related evaluations.

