	N	%	N	%	N	%	N	%
1. Do you like the appearance design of this product?								
2. Do you find it easy to use this product ?								
3. Using self -testing to screen for HPV will increase your willingness to do HPV screening regularly ?								
4. Would you like to use this product again next time ?								
5. Would you like to recommend relatives and friends to use this product ?								
6. May I ask you, is the process of putting this product into the vagina for sampling easy ?								
7. Do you think the process of using this product for inspection is safe ?								
8. Do you feel comfortable after using this product ?								
9. Is the instruction manual of this product easy to understand ?								

Table 11 Self -sampling Illustrative Video Questionnaire (N = , ITT)

Self- Sampling Instructions Video Questionnaire	yes		no	
	N	%	N	%
1. Can I use the self -testing stick to take samples during the menstrual period? sampling stick to sample when there is a lot of mucus secretion during the ovulation period?				

Table 12 Adverse events related to experimental medical materials (N = , ITT)

Patient	Adverse Events	Grade	Onset Time	Duration Related SAE

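### The study nurse who receives the specimen also helps with the self-sampling questionnaire and takes it back, with no limit on or record of the help, so the Table 10 ratings may be influenced

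*Protocol*

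**What the plan says.** The Protocol, Study design and methods, describes two occasions on which a woman answers questions.

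- **Before sampling.** Item C says of the self-learning materials: "Participants will then answer a questionnaire to verify the clarity of the instructional materials". E.3(1) says of the women: "They must read the instruction manual, watch an instructional video, and confirm their understanding by answering questions". Neither place mentions help from a nurse.
- **At hand-over of the self-collected specimen.** E.3(3) says "the study nurse asked the subjects to complete the self-sampling questionnaire in the case report form and provided assistance", and continues: "After the subjects fill out the questionnaire, the research nurse will take back the case report form".

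The SAP, Secondary evaluation indicators to be analyzed, item G, gives the source of the satisfaction results: "Use the subject questionnaire in the case report form to collect the survey data". These results fill Table 10, which has nine items rated from very low to very high. They cover ease of use, comfort afterwards, willingness to recommend and whether the manual is easy to understand.

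Item D of the same SAP section splits the usability objective in two. For effective sampling, "The beta-globin of the test results will be used as an evaluation index for valid specimens". The questionnaire survey is used for the explanatory files. Table 11, titled "Self -sampling Illustrative Video Questionnaire (N = , ITT"), reports yes/no answers to knowledge questions about the video. Neither table has a place for whether the woman was helped.

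**The concern.** One staff role hands over the swab, receives the specimen, asks for the ratings, helps with them and collects them. A woman rating a product in front of the person who gave it to her, and who will see her answers, may be more polite than she would be alone. Help of unspecified content adds a second route: an explanation of the manual given while the form is being completed can raise the rating of the manual itself.

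Satisfaction is secondary objective 5. The questionnaire part of secondary objective 1, on the instructions, also draws in part on Table 10 through its item on the manual. If the help shifts answers, a good score cannot be credited wholly to the kit and its materials. Because nothing is recorded, nobody could examine this afterwards.

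**Working it through.** The plan states no figure that depends on how the questionnaire is administered, so there is nothing to reproduce. The check has two parts.

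**1. Which outputs does E.3(3) reach?**

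| Output | Link to the assisted form | Conclusion |
|---|---|---|
| Table 10, satisfaction | SAP item G names the questionnaire in the case report form; E.3(3) names the self-sampling questionnaire in the case report form | Reached |
| Table 11, video questions | Could come from E.3(1), before sampling and with no help mentioned, or from the hand-over form | Not settled |
| Self-sampling success rate | Laboratory beta-globin result; help comes after the swab is in the tube | Not reached |
| Primary kappa | Laboratory HPV results on valid pairs | Not reached |

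**2. How large could the effect on Table 10 be?**

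The documents give neither the share of women helped nor the effect of help. Both are assumed here: share *s* from 10% to 100%, and shift *d* among those helped from 5 to 20 percentage points. Take the proportion answering favourably (high or very high).

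Shift in the reported proportion = *s* × *d*:

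- 10% × 5 points = 0.5 points
- 25% × 10 points = 2.5 points
- 50% × 10 points = 5 points
- 100% × 20 points = 20 points

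For scale, the 95% half-width with all 1,200 planned women responding is 1.96 × √(p(1 − p)/1,200):

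| Proportion favourable | Half-width |
|---|---|
| 50% | 2.8 points |
| 80% | 2.3 points |
| 90% | 1.7 points |
| 95% | 1.2 points |

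The smallest shift lies inside every one of these half-widths, and the 5-point and 20-point shifts lie outside all of them. The 2.5-point shift exceeds all but the one at 50%.

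**Table 11, only if it is on the assisted form.** Suppose 85% would answer an item correctly unaided and every helped woman ends with the correct answer, which is the extreme case. The table would then show (1 − *s*) × 85% + *s*:

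- *s* = 10%: 0.90 × 85% + 10% = 86.5%
- *s* = 30%: 0.70 × 85% + 30% = 89.5%
- *s* = 60%: 0.40 × 85% + 60% = 94%

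The half-width at 85% is 1.96 × √(0.85 × 0.15/1,200) = 2.0 points. The first case (1.5 points above 85%) is inside it; the other two (4.5 and 9 points) are outside.

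**The case against.** The strongest reply is that E.3(3) describes ordinary help with a form. Its next sentence has the women filling in the questionnaire, so help may mean reading an item aloud, explaining a term or checking for blanks. Nothing shows a nurse supplying or steering an answer. Tables 10 and 11 are descriptive, with no hypothesis or success threshold attached. All of this stands, and it keeps the point minor.

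Three stronger readings are tempting, and the documents do not support them.

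- **That E.3(3) contradicts design item B.** Item B reads: "The trial aims to assess how well regular women can collect specimens using self-collection kits without professional assistance". It concerns collecting the specimen. Help with a form after sampling does not make the sampling assisted.
- **That both tables are biased upward.** For Table 10 the direction is plausible but cannot be derived. For Table 11 even the link to the assisted form is open, and its title and content fit the earlier comprehension step at least as well.
- **That secondary objectives 1 and 5 both rest on these tables.** Objective 1 is carried mainly by beta-globin validity. The questionnaire addresses only the instructions.

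The objection does not remove the core: the Table 10 ratings come from a form completed with unlimited, unrecorded help and returned openly to the helper.

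A further caution concerns the remedy. Making unassisted women the main result would drop those who needed help, plausibly the ones who find the materials hardest. That could itself raise the scores, and it departs from the ITT population that both documents set for satisfaction.

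**Conclusion.** The point holds as an inexpensive improvement to secondary, descriptive results. As written, the procedure exposes Table 10 to courteous or prompted answers, probably in the kit's favour. Table 11 is exposed only if its questions are on the hand-over form. The size is unknown: the illustrated range of 0.5 to 20 points rests wholly on assumed shares and shifts and shows only that the effect could be negligible or well beyond sampling error. The half-widths assume that all 1,200 women respond. The success rate of self-sampling and the primary agreement analysis are unaffected.

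**What to change.** 1. Change Protocol E.3(3) so that the woman completes the rating items herself and returns them in a sealed envelope with the specimen. Limit nurse help to reading items aloud, and add an assisted yes/no box to the case report form.
2. State in both documents that the Table 11 answers are the woman's first unaided answers at the E.3(1) step, before sampling.
3. Keep all ITT respondents as the main result in Tables 10 and 11. Show assisted and unassisted women alongside as a descriptive check only, since women who need help may differ from those who do not.

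Cost: a few sentences, one tick-box and extra columns in two tables, with no added staff. A nurse can no longer spot gaps at hand-over, so the completeness review of these items moves to data entry and a few more will stay blank. The reported satisfaction score may be slightly lower.

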#### **Secondary evaluation indicators:**

- A. The success rate of HPV typing (proportion of effective specimens) for physician-collected and self-collected specimens.
- B. of all detectable HPV types.
- C. The incidence of adverse reactions is used as a safety evaluation index to evaluate whether adverse reactions will occur when a doctor's examination or a woman's self-sampling of vaginal secretions will occur. The test process is recorded according to the CTCAE version 5.0 grading standards
- D. Evaluate whether women can complete effective self-sampling by following the instructions or videos. The beta-globin of the test results will be used as the evaluation index of the effective specimen, and the results of the questionnaire survey will be used to evaluate the reliability of the description file.
- E. The self-collection success rate (proportion of effective specimens) and consistency assessment of each group under the test group.
- F. Correlation between the HPV test results collected by doctors, the HPV test results of self-collected specimens, and the cervical smear and histopathological diagnosis results at the same time. Taking the most severe pathological diagnosis as the standard, calculate separately
- 1. Sensitivity, specificity, positive predictive value and negative predictive value for predicting cervical lesions based on HPV test results collected by physicians
- 2. Sensitivity, specificity, positive predictive value and negative predictive value for predicting cervical lesions based on test results of self-collected specimens
- G. Through questionnaires, subjects' self-sampling satisfaction was assessed.

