- (2) The high-risk HPV test results are inconsistent (disagreement). One of the samples collected by the doctor or self-collected does not have any of the above-mentioned high-risk HPV types, and the other has any of the above-mentioned high-risk types.
- 2. The consistency between the test results of the specimens collected by the physician and the specimens collected by the subjects will be evaluated by Cohen 's kappa coefficient or related test comparisons.
- C. The consistency assessment will use valid samples as the analysis group, that is, the samples collected by the verification physician and the self-collected specimens of the same subject are both valid samples. Valid specimens are defined as those who test positive for the  $\beta$ -globin gene in the internal control group of the [name] Papillomavirus Genotyping Test Kit.
- D. Safety, self-sampling success rate, and satisfaction evaluation are based on the intent-to-treat population (ITT).

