### **Secondary evaluation indicators:**

- A. The success rate (proportion of effective specimens) of HPV typing in physician - collected and self- collected specimens of all detectable HPV types.
- B. The incidence of adverse reactions was used as the safety evaluation index to evaluate whether there would be adverse reactions caused by doctors' self-examination of vaginal secretions or self-examination of vaginal secretions. The test process was recorded according to the grading standard of CTCAE version 5.0 .
- C. Evaluate whether women can complete effective self-specimen sampling by following the instructions or videos. The beta-globin of the test results will be used as an evaluation index for valid specimens, and the reliability of the explanatory files will be evaluated by the results of the questionnaire survey.
- D. -collection success rate (proportion of effective specimens) and consistency evaluation of each group under the test group .
- E. The correlation between the HPV test results collected by physicians , the HPV test results of self- collected samples, and the results of Pap smear and histopathological diagnosis at the same time . Taking the most serious pathological diagnosis as the standard, calculate
  1. Predict the sensitivity, specificity, positive predictive value and negative predictive value of cervical lesions based on the HPV test results of the samples taken by doctors
  2. Predict the sensitivity, specificity, positive predictive value and negative predictive value of cervical lesions based on the test results of self- collected samples
- F. The questionnaire was used to evaluate the satisfaction of the subjects' self-testing .

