agreement (chance agreement). The standard error of the Kappa statistic is based on Fleiss, Cohen, and Everitt (1969) as  $SE(K) = SD(K)/\sqrt{N}$ , where  $SD(K) = \sqrt{P_0(1 - P_0)/(1 - P_c)^2}$ . The 100(1- $\alpha$ )% interval estimate of the Kappa statistic is  $K \pm z_{\alpha/2} SE(K)$ .

		Physician check		sum
		High-risk HPV detected	No high-risk HPV detected	
self - test	High-risk HPV detected	a	b	rm1
	No high-risk HPV detected	c	d	rm2
	sum	cm1	cm2	no

For each HPV type ( type-specific) , the consistency between the test results of the samples collected by the physician and the samples collected by the subjects will be evaluated by Cohen 's kappa coefficient or compared with related tests.

- G. Consistency assessment will take valid samples as the analysis group, that is, the same subject's verification physician and self- sampling samples are all valid samples.
- H. A valid sample is defined as a positive test for the  $\beta$ -globin gene in the internal control group of Jingyu Human Papillomavirus Genotyping Detection Kit . The intent-to-treat group (ITT) was used as the analysis group for safety, self- collection success rate, and satisfaction evaluation.

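### No limit is set on the time between physician sampling and self-sampling, so a real change in HPV status in the gap counts as disagreement and lowers the primary kappa

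*Protocol*

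**What the plan says.** The physician's specimen is taken at the outpatient visit (protocol, Study design and methods, E.2(1)). For the self-sample, E.3(4) says: "Subjects can self-sampling on the day of the outpatient clinic or thereafter". Two limits follow in the same item:

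- Intervening care: "no biopsy, medicine, surgery or any form of treatment is allowed between the subject's self-sampling and the doctor's sampling".
- Hand-over: "Specimens must be sent to the study nurse within one week of collection". This clock starts at self-collection, so it limits storage and transport, not the gap between the two samplings.

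The primary analysis set is defined by specimen validity alone. Protocol, Statistical methods, item C: "The consistency assessment will use valid samples as the analysis group". SAP, Statistical considerations, item G: "Consistency assessment will take valid samples as the analysis group". In both documents a valid specimen is one that is beta-globin positive. Any pair with one high-risk positive and one high-risk negative result is inconsistent, whatever the time between the specimens.

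The SAP has no interval criterion, no summary of the interval and no analysis by interval, and its table shells have no place for one.

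**The concern.** The primary kappa is meant to show whether two ways of collecting a specimen give the same answer for the same woman. That requires her infection status to be the same at both samplings. The ban on intervening care guards against change caused by treatment. It does not guard against clearance or new infection in an untreated, fully eligible woman. If her status changes between the samplings, both specimens can be correct and the pair is still counted as disagreement.

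The planned margin is narrow: a kappa of 0.72 is assumed, and the trial must show more than 0.66. A small amount of real change could make a kit that performs as planned miss its target. If collection dates are not available for analysis, a disappointing kappa could not be separated into kit error and elapsed time.

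Only a change between high-risk positive and high-risk negative matters here. A switch from one high-risk type to another affects the type-specific tables only.

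**Working it through.** **Inputs from the documents.** Overall positivity 67% (protocol, Statistical methods; 0.10×0.1 + 0.15×0.7 + 0.20×0.5 + 0.20×0.7 + 0.35×0.9 = 0.67). Null kappa 0.66 (SAP, Test Hypothesis and Verification). Assumed kappa 0.72, power 80%, level 0.05, 1,049 cases needed, up to 10% loss, 1,200 recruited (SAP, Sample size calculation).

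**Reproducing 1,049.** With equal margins, chance agreement is Pc = 0.67² + 0.33² = 0.5578. The sample size is n = [(1.645·SD0 + 0.842·SD1)/(0.72 − 0.66)]². The full Fleiss-Cohen-Everitt large-sample SD at kappa 0.66 and 0.72 gives n = 1,048.2, so 1,049. The SAP does not say whether the level is one- or two-sided; one-sided reproduces the figure, while two-sided gives 1,339.

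**Width of the margin.** Observed agreement is Po = Pc + kappa·(1 − Pc).

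- Kappa 0.72: Po = 0.5578 + 0.72×0.4422 = 0.8762, so 12.4% of pairs disagree.
- Kappa 0.66: Po = 0.5578 + 0.66×0.4422 = 0.8497, so 15.0% disagree.
- Difference: 2.65 percentage points of pairs.

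**Starting table at kappa 0.72.** Both positive 0.608, each discordant cell 0.062, both negative 0.268.

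**Effect of a change in status (assumed).** Let x be the share of all women whose status changes between samplings, that is, the share late times the share of those who change. For example, 10%×5% = 0.5%, 20%×5% = 1%, 20%×10% = 2%. Change is taken to be unrelated to whether the pair would otherwise have agreed. Not every change adds a discordant pair, because some changers come from pairs that already disagree, and their change restores agreement. Net added discordance is:

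- clearance only: x·(0.608 − 0.062)/0.67 = 0.82x (0.815 before rounding);
- equal mix of clearance and new infection: ½×0.815x + ½×x·(0.268 − 0.062)/0.33 = 0.72x.

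**One case in full (x = 1%, clearance).** The clearance rate among positives is 0.01/0.67 = 0.0149. Po falls to 0.8762 − 0.0082 = 0.8680. Self-sample positivity becomes 0.66, so Pc = 0.66×0.67 + 0.34×0.33 = 0.5544. Kappa = (0.8680 − 0.5544)/0.4456 = 0.704.

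**Results at n = 1,049** (multinomial simulation, one-sided 0.05, full variance estimated from each simulated table; clearance-only and mixed change agree within about one point):

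| Share of women who change | Expected kappa | Power |
|---|---|---|
| 0 | 0.72 | about 82% |
| 0.5% | 0.71 | about 71% |
| 1% | 0.70 | about 58% |
| 2% | 0.69 | about 32% |

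The simulated start is 82% rather than 80% because the test uses the estimated variance instead of the null variance.

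**Cross-check by formula with the null variance.** Suppose 25% of women sample late, and among them 5% of positives clear and 2% of negatives acquire. Then 0.25×(0.67×0.05 + 0.33×0.02) = 1.0% of women change; kappa is 0.704 and power 55%, against 80% with no change. Expected kappa reaches 0.66 when about 5.7% of positives clear, or when about 3.7% of all women change in either direction.

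**The case against.** **Contradiction between passages.** A reader might infer that the protocol contradicts itself. E.3(2) says that "subjects will place the swab in the collection tube and hand it to the study nurse", which can sound like a single visit, and the accuracy endpoint refers to "the cervical smear and histopathological diagnosis results at the same time" (SAP: "the results of Pap smear and histopathological diagnosis at the same time"). The documents do not support this. E.3(2) names no day and is compatible with E.3(4). The timing phrase in the accuracy endpoint can attach to smear and histology alone. What stands is an interval without an upper limit.

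**Larger power losses.** A reader might count every change of status as a new discordant pair. That would give power of 66-69%, 48-52% and 16-22% for the three rates. These figures are too low, because they ignore the changers who come from pairs already in disagreement.

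**The ban on intervening care.** Groups 4 and 5, 55% of recruitment (660 women), are defined as not yet treated, so barring care between samplings limits long gaps there in practice. This is fair, but the ban sets no number of days. Nothing in the text calls for an early self-sample in groups 1 to 3 (45%, 540 women).

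**Unknown size.** The documents give no share of late samples and no rate of change, and over a delay of days the change could be close to nil. This stands, and it is why the power figures are scenarios and not predictions.

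**Direction.** The bias is conservative for the primary hypothesis. This also stands: the risk is a missed success. For Table 9, the self-collected and physician columns could refer to different times, but neither the direction nor the size of any effect can be derived from the documents.

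**Conclusion.** The concern holds as a gap in the sampling rule and in the analysis plan. Self-sampling at any later date is permitted, and every beta-globin-valid pair enters the primary table whatever the interval. Real change in the gap lowers kappa against the kit. The size depends on assumed rates: from zero, if all women sample on the clinic day, to a loss of about 50 points of power (82% to 32%) if 2% of all women change status. The figures rest on 67% positivity, equal margins before any change, a one-sided 0.05 level, and change unrelated to prior agreement.

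It should not be read as a contradiction between passages, as a route to a false positive trial, or as evidence that collection dates go unrecorded. The case report form is not among the documents.

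**What to change.** - In protocol E.3(4), state a maximum interval between physician sampling and self-sampling. The sponsor chooses its length.
- Make sure that both collection dates are captured and available for analysis.
- Keep all valid pairs as the primary consistency set (SAP items G and H).
- Before the self-sample codes are opened, pre-specify a supportive kappa in Table 4 limited to pairs within the interval, and a matching analysis for Table 9.

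**Cost.** One added procedural limit for sites and one extra analysis. The planned sample size does not change.

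Removing late pairs from the primary set is not advised. After the planned 10% loss, 1,200×0.9 = 1,080 pairs remain, only 31 above the 1,049 required. If 10% or 20% of them were late and fell outside the interval, 108 or 216 would go, leaving 972 or 864. At kappa 0.72 the formula that gives 80% at 1,049 gives about 77% or 73% there. Removal could win power back if change were frequent, but that rate is unknown while the loss of pairs is certain.
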